### **7.7.3.1.2 Analyses of secondary outcomes**

The analysis of spontaneous abortion (SAB) and stillbirth: Only those subjects who are enrolled prior to 20 weeks of gestation are eligible for the analysis of SAB. Since they are not followed from gestational age zero, survival analysis methods will be used to handle left truncation, as well as right-censoring when a subject is lost-to-follow-up prior to 20 weeks' gestation. Left-truncated Kaplan-Meier estimate at 20 weeks' gestation will be used to estimate the SAB rate in each of the cohorts (Tsai et al, 1987). The Cox proportional hazards regression models incorporating left truncation will be used to estimate the hazard ratio (HR) of different cohorts, as well as to obtain the 95% CIs. Stillbirth will be analyzed in a similar fashion. To account for potential confounding, PS methods described above will be applied, where regression adjustment will be used with the Cox model to obtain the adjusted HR.

The analysis of premature delivery: Only those subjects who are enrolled prior to 37 weeks of gestation are eligible for the analysis of premature delivery. These data will be analyzed similarly to SAB, as described above, using survival analysis methods to handle possible right-censoring.

The following will be considered binary endpoints: preeclampsia/eclampsia, small for gestational age (SGA) at birth in weight, height and head circumference, respectively, and growth deficiency at about one year of age in weight, height and head circumference respectively. The analysis of each of these outcomes will be similar to the analysis of the primary outcome, based on all pregnancies resulting in live born infants excluding twins or higher order multiples.

Multiple births will be included in the analyses of minor structural defects, ASQ, and serious or opportunistic infections. These outcome variables will thus likely contain correlated data due to twins or higher order multiples, and the generalized estimating equations (GEE) approach will be used (Liang and Zeger, 1986, Diggle et al, 2002).

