## 7.2 Setting

The Pregnancy Exposure Registry is sponsored by Novartis (referred later as “Sponsor”) and conducted by the Organization of Teratology Information Specialists (OTIS) Research Group, a network of university and health department based telephone information centers serving pregnant women and healthcare providers throughout North America ([Leen-Mitchell et al, 2000](#)). These services receive spontaneous telephone inquiries from women and healthcare providers about the safety or risk associated with environmental exposures in pregnancy, including medications. Trained Teratogen Information Specialists at each site provide appropriate risk assessment and referral for all patient and healthcare provider callers free of charge. These services also provide a basis for collaborative research such as this Registry. Thus, individual Teratogen Information Services located throughout the US and Canada will serve as a source of referrals not only for siponimod-exposed pregnancies but also for similarly ascertained disease-matched comparison pregnant women who have not used siponimod in pregnancy and similarly-ascertained healthy pregnant women who have no diagnosis of the approved indication, have not had exposure to a known human teratogen, and have not taken siponimod in pregnancy.

Organization of Teratology Information Specialists member services receive over 70,000 teratogen information inquiries per year, therefore OTIS members constitute a major source of identification and recruitment of exposed women and appropriate comparison women. Once women are in contact with the OTIS Research Center, enrollment in the Registry is voluntary and requires informed consent of the pregnant woman. The Registry encourages enrollment as early in the pregnancy as possible, before any prenatal testing results are known. This is accomplished by encouraging clinicians to refer patients, and patients who contact an OTIS service or who self-refer, to enroll upon first positive pregnancy test. These efforts reduce possible bias based on prior knowledge of a normal or abnormal ultrasound and allow for better estimation of risk of spontaneous abortion.

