**Table 7-2 Timing of Cohort Enrollment, Interviews, Examinations, and Medical Records**

	Anytime In Pregnancy	20-22 Weeks' Gestation b	32-34 Weeks' Gestation c	0-6 Weeks Post-Delivery	0-12 Months Post-Delivery	1 Year Post-Delivery
Referral a	√					
Enrollment and Consent a	√					

Enrollment Interview a	√					
Interim Interview I		√				
Interim Interview II			√			
Pregnancy Outcome Interview and Request for Medical Records				√		
Medical Record Review					√	
Dysmorphology Examination					√	
Developmental Screening / ASQ						√
Pediatric 1-Year Medical Records Request and Review						√

aParticipants may enroll in the study anytime during pregnancy

bIf subject is enrolled and Intake Interview is conducted after 18 weeks' gestation, only one interim interview will be conducted during pregnancy at 32-34 weeks gestation

cIf subject is enrolled and Intake Interview is conducted at 30 weeks' gestation or after, no Interim Interview will be collected

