### 7.5.1 Determination of sample size

The sample size for this study is not only based on the statistical considerations to address the question of interest but also takes into account the feasibility aspects, prior experience and available literature ([Krueger et al 2017](#)) on conduct of pregnancy registries in the MS disease area.

In the three cohorts, approximately 867 pregnant women will be enrolled in US and Canada with a ratio of 1:1:1.

Based on previous experience with MotherToBaby/OTIS Pregnancy Studies, it is estimated that subjects will be an average of 7-10 weeks post-LMP at the time of enrollment. Given this mean gestational timing at enrollment, the anticipated spontaneous abortion/stillbirth rate is 10%, the estimated elective abortion rate is 5%, and the estimated lost to follow-up rate is 5% ([Chambers et al, 2016](#)). This will result in known outcomes for approximately 273 pregnancies in each cohort, including 231 pregnancies with at least one live born infant in each cohort at the end of recruitment.

Baseline rates of major structural birth defects, specific patterns of three or more minor structural defects, premature delivery, and small for gestational age are based on previous MotherToBaby/ OTIS studies and on general population data. Rates of spontaneous abortion in the general population are 15-20% ([Avalos AL, et al 2012](#), and [Magnus et al 2019](#)). However, since women do not typically enroll in pregnancy registries until after 7-8 weeks' gestation when the highest risk of spontaneous abortion has passed, the baseline estimate is drawn from previous OTIS studies. [Table 7-4](#) gives the minimum detectable effect sizes with 80% power (two-sided significance level 0.05, except as noted below for pattern of minor structural defects), for the comparisons described above. If the disease-matched comparison and the healthy comparison groups are comparable, then consideration will be given to pooling data in the two comparisons cohorts for analysis, as shown in [Table 7-5](#). The current sample size provides 80% power to detect a risk ratio of approximately 4.4 or greater in major structural defects compared to the baseline prevalence of 3% in the comparison groups. This is consistent with the population prevalence of major structural defects of 2.8% in the Atlanta metropolitan area ([CDC 2017](#)).

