## **7.9 Limitations of the research methods**

The primary limitation of a cohort study utilizing volunteer subjects is potential selection bias. The use of comparably selected unexposed pregnancies will address this concern to some extent. However, women who agree to enroll in the cohort study may represent particularly high or low risk pregnancies ([Johnson et al, 2001](#)). The study results will be strictly generalizable to women fitting the profile of the sample of women who enroll.

Another limitation of the study design relates to the evaluation of spontaneous abortion rates. Rates of early spontaneous abortion, i.e., at 7-9 weeks post-LMP or less, will not be measured in a study that enrolls women after recognition of pregnancy. The study results with respect to spontaneous abortion/miscarriage will be limited to relative risk for late first-trimester and early second-trimester pregnancy loss. The subset of participants who are eligible for this analysis is restricted to those who enroll prior to 20.0 weeks' gestation. Although it has not been the OTIS experience in previous studies, if a high proportion of women enroll in the study after 20.0 weeks' gestation, the statistical power for detecting risks of spontaneous abortion/miscarriage

will be reduced. In addition, if a high proportion of women enroll later in pregnancy, other survival biases may be introduced. A sensitivity analysis by gestational age at enrollment will be performed in order to address these questions.

Because early prenatal testing is so prevalent in the US and Canada, it may be difficult to achieve adequate numbers of patients if all pregnancies with prior prenatal testing are excluded from the analysis. Therefore, the Registry will include pregnancies enrolled prior to outcome but after a prenatal test has been performed as long as the test does not indicate the presence of a major structural defect. The FDA guidance document ([FDA Draft Postapproval Pregnancy Safety Studies; Guidance for Industry](#)) acknowledges that such an approach may be necessary to accrue adequate numbers. However, this practice could potentially bias the results by lowering the overall estimate of the prevalence of birth defects ([Honein et al., 1999](#)). The data analysis will address this in each interim and the final study report by sub-analysis stratifying on use of prenatal diagnostic testing.

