Given the Phase III data supporting the siponimod approval for relapsing forms of MS was generated in the SPMS population, as reflected in the clinical studies section of the FDA approved labelling, it may transpire that siponimod is more likely to be prescribed to patients

who are older and with higher disability. Thus there is potential for channeling bias. To the extent that factors such as age and disability differ in exposed and comparison cohorts, these will be considered in adjusted analyses.

It is possible that women in the disease comparison group may have less severe disease than those who enroll in the siponimod exposed group. It is also possible that women in the siponimod exposed group will enroll earlier in pregnancy than either of the comparison groups. The study will monitor disease severity and gestational age at enrollment and discuss any modifications needed in recruitment strategies as the study progresses. Further, all three cohorts rely on volunteers and may not represent the entire population of exposed and unexposed women.

Although all possible efforts will be made to retain participants in the registry or follow up with their healthcare providers, some participants will be lost during follow up. It could be possible that participants lost during follow up and with missing data on outcomes may be different compared to those with complete follow up data. In previous OTIS studies, lost-to-follow-up rates have been low, typically <5%. However, the characteristics of women lost to follow up will be compared to those who are retained in order to understand the direction and magnitude of the bias due to loss to follow up.

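### The spontaneous abortion rate in each cohort has no common starting week, so the reported rates can be unstable and can cover different gestational windows

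*Protocol*

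**What the plan says.** Section 7.7.3.1.2 gives the estimator for spontaneous abortion (SAB): "Left-truncated Kaplan-Meier estimate at 20 weeks' gestation will be used to estimate the SAB rate in each of the cohorts". Eligibility is bounded only from above: "Only those subjects who are enrolled prior to 20 weeks of gestation are eligible for the analysis of SAB". Cohorts are then compared by a different tool: "The Cox proportional hazards regression models incorporating left truncation will be used to estimate the hazard ratio (HR) of different cohorts".

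Entry has no lower bound. A note to Table 7-2 says "Participants may enroll in the study anytime during pregnancy", and section 7.2 describes encouraging women "to enroll upon first positive pregnancy test". Section 7.5.1 nevertheless expects that "subjects will be an average of 7-10 weeks post-LMP at the time of enrollment".

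Section 7.9 states the scope: "Rates of early spontaneous abortion, i.e., at 7-9 weeks post-LMP or less, will not be measured". It restricts the SAB result to losses in the late first and early second trimester. It also says "It is also possible that women in the siponimod exposed group will enroll earlier in pregnancy than either of the comparison groups", and it plans a sensitivity analysis by gestational age at enrolment.

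**The concern.** Under delayed entry, the product-limit estimate multiplies conditional survival over every loss after the first woman enters. With no stated start, the first entrant in each cohort decides where the curve begins. Two problems follow.

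- **Thin early risk sets.** If average entry is at 7-10 weeks and some women join at the first positive test, a few women carry the early weeks. One loss among them moves the 20-week figure a great deal.
- **Unequal windows.** If one cohort's first entrants come earlier than another's, the two rates answer different questions. Miscarriage risk is concentrated in early weeks, so the earlier-starting cohort shows the higher rate with no drug effect.

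SAB prevalence is to be estimated and compared between cohorts (section 6), so these rates will be read side by side in a safety report. The estimator also takes in the early period that 7.9 places outside the study's reach.

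**Working it through.** **The plan's own figure.** Table 7-4 gives 80% power for SAB/stillbirth at 259 per group, 10% in the comparison group and a relative risk of 1.9 (10% v 19%). Exact enumeration of Fisher's test, two-sided 0.05, gives 80.2%. That row reproduces and is not in question.

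**Leverage of one early loss.** This needs no hazard model. If one loss occurs in an early risk set of r women and the remaining loss to 20 weeks is 10%, the estimate is 1 - (1 - 1/r) x 0.90.

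| r | 20-week rate |
|---|---|
| 1 | 100% |
| 2 | 55% |
| 3 | 40% |
| 5 | 28% |
| 10 | 19% |
| 50 | 11.8% |

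**How the target depends on the start.** Assume 18% total loss from week 4 (inside the 15-20% general-population range in 7.5.1) and a hazard falling exponentially at d per week. The share of cumulative hazard left from week k is (exp(-d(k-4)) - exp(-16d)) / (1 - exp(-16d)), and total cumulative hazard is -ln(0.82) = 0.198.

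- d = 0.15, from week 7: share 0.60, loss 1 - exp(-0.119) = 11.3%. From week 8 it is 9.5%.
- d = 0.30, from week 7: share 0.40, loss 1 - exp(-0.080) = 7.7%.

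A cohort starting at week 4 set against one starting at week 7 therefore has a true ratio of 18.0/11.3 = 1.6 or 18.0/7.7 = 2.3, with identical hazards.

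**Simulation with no drug effect.** There were 259 women per cohort, 1,000 runs and gamma-shaped entry. The early cohort had mean entry 7.5 weeks and earliest week 4; the late cohort had mean 10 weeks. Each pair of results is for d = 0.15 / d = 0.30.

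| Scenario | Mean rates, early v late | Median ratio | Ratio 1.9 or more |
|---|---|---|---|
| Same timing in both cohorts | 16.5 v 17.0% / 16.4 v 16.0% | 0.98 / 0.98 | 8% / 16% |
| Late cohort's earliest week also 4 | 17.9 v 15.9% / 17.2 v 14.0% | 1.20 / 1.48 | 18% / 35% |
| Late cohort's earliest week 7 | 17.6 v 10.8% / 17.4 v 7.5% | 1.60 / 2.34 | 32% / 65% |
| Common week-8 start, unequal timing | about 9.5% each / 5.7-5.8% each | 0.98-1.02 | 3-11% |

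The last row covers the two scenarios with unequal timing. A milder case, with earliest entry in week 6 and mean entry 8 v 10 weeks, gave a median ratio of 1.11. At 20% total loss and the steeper decline, the week-4 v week-7 case gave 2.41.

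**Spread of a single cohort's rate, about 260 women.** The SD is about 10-11 points with entry from week 4, 5-7 from week 6 and 2 from week 7, against 1.5-2.2 from a week-8 start. Mean entry matters too. Across the week-4 runs the SD ranged from about 5 to 13 points. With earliest week 6, mean 8.5 and entry SD 2.5 weeks, it was 3.2. The 2-point figure for week 7 has mean entry 8.5; with mean entry 10 weeks the SD is about 5.

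**Cox model on the same data (500 runs per scenario).** Median hazard ratio 0.97-1.03; rejection rate 3.6-5.2% at the 5% level.

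**The case against.** - **The start of a delayed-entry curve is commonly fixed in the SAP, and the SAP is not shown.** This is fair, and the SAP may set one. But the protocol does more than name a method. It fixes the estimator, the read-out week and the upper entry limit, and read literally the result does not match the scope in 7.9.
- **The comparison is the Cox hazard ratio.** This stands. A reader might infer that the study would find a false SAB signal for siponimod. The documents do not support that: the Cox model compares women at the same gestational age, and no ratio of Kaplan-Meier rates is planned. The harm is confined to the reported rates and to reading them side by side.
- **Different enrolment timing does not in itself bias the estimator.** This also stands. A reader might infer that any difference in average enrolment week distorts the rates. With well-filled risk sets from the same first week, both cohorts estimate the same quantity; divergence needs thin early risk sets or different earliest weeks.
- **The large figures need entry from week 4, while 7.5.1 says women typically enrol after 7-8 weeks.** This is largely right, and estimates of exactly 100% were rare (0-1.4% of simulated cohorts). But earlier entry is allowed and encouraged, and a cohort averaging 7 weeks must include some women before week 7 unless all join then.
- **Enrolment timing is already addressed.** Section 7.9 plans monitoring and a sensitivity analysis by gestational age at enrolment, and Table 7-1 lists it as a confounder. These help, but none gives the reported rate a common start.

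**Conclusion.** The point holds for the per-cohort SAB rate only. As written, that rate starts wherever each cohort's first entrant happens to be, can rest on very few women in the early weeks, and reaches into a period that 7.9 says is not measured. The leverage table is plain arithmetic. The remaining sizes rest on an assumed hazard shape and entry distribution: SD from about 2 points (earliest entry week 7, mean 8.5) to about 10-11 points (week 4), and a null ratio of rates of about 1.1 to 2.3, slightly more at 20% total loss. Every scenario with earlier exposed enrolment pointed the same way, and a common start removed the difference. The Cox hazard ratio is sound on this point. Because SAB is a secondary outcome and its planned comparison is intact, this is a worthwhile correction to a descriptive safety figure and does not threaten the study's inference.

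**What to change.** In 7.7.3.1.2, define the per-cohort SAB rate as the conditional probability of SAB from one gestational week to 20 weeks, the same week in every cohort and fixed blind to outcome. Eight completed weeks is one option; another is the first week at which every cohort's risk set reaches a stated minimum. Keep delayed entry after that week, and report earlier losses by count. Leave the Cox model unchanged. An unrestricted model still uses losses before the starting week, so its hazard ratio should not carry that window as a label unless the model is restricted to it.

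The cost is a sentence or two of text and no new data. Losses before the starting week drop out of the rate, but 7.9 already says that early losses are not measured.

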## 6 Research question and objectives

The purpose of the Siponimod Pregnancy Exposure Registry is to evaluate the effect of siponimod exposure on rates of pregnancy and infant outcomes in exposed pregnancies compared to unexposed disease-matched and healthy unexposed pregnancies. The lack of human fetal safety data for siponimod makes such a monitoring system an important component of epidemiologic research on the safety of this drug.

The primary objective is to estimate and compare the prevalence of major structural defects in siponimod exposed pregnant women versus 1) disease-matched pregnant women not exposed to siponimod, and 2) healthy pregnant women.

The primary objective will be evaluated among i) pregnancies ending in at least one live birth, and ii) pregnancies ending in at least one live birth, spontaneous abortion, still birth or termination of pregnancy

Secondary objectives are to estimate and compare the prevalence of selected adverse pregnancy and infant outcomes in siponimod-exposed pregnant women versus 1) disease-matched pregnant women not exposed to siponimod, and 2) healthy pregnant women.

Mayzent exposure is defined as exposure to siponimod any time from the 4th days post the first day of LMP prior to conception up to and including the end of pregnancy.

- The primary outcome of the study is major structural defects.
- The secondary outcomes of the study are:
  - Spontaneous abortion/miscarriage
  - Stillbirth
  - Elective termination
  - Preterm delivery
  - Preeclampsia / eclampsia
  - Pattern of 3 or more minor structural defects
  - Small for gestational age
  - Postnatal growth small for age at approximately one year of age
  - Developmental performance at approximately one year of age
  - Serious or opportunistic infections in the first year of life.

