#### **7.7.2.4 Outcome classification for secondary outcomes**

- ***Spontaneous abortion:*** spontaneous abortion/miscarriage is defined as non-deliberate fetal death which occurs prior to less than 20.0 weeks post-LMP.
- ***Analysis subset:*** the analysis subset for the secondary outcome of spontaneous abortion will be restricted in Cohort 1 to those who were exposed to any dose from

the 4th day post first day of LMP prior to conception to 20 weeks' gestation and enrolled prior to 20 weeks' gestation. The analysis subset for cohorts 2 and 3 will be restricted to those who enrolled prior to 20 weeks' gestation.

- **Stillbirth:** stillbirth is defined as non-deliberate fetal death anytime in gestation at or after 20 weeks post-LMP.
- **Elective termination:** elective termination/abortion is defined as deliberate termination of pregnancy at any time in gestation. Reasons for elective abortions are captured and are classified as due to medical reasons or social reasons.
- **Premature delivery:** premature delivery is defined as live birth prior to 37.0 weeks gestation as counted from LMP (or calculated from first-trimester ultrasound-derived due date if last menstrual period uncertain or more than 1 week discrepant). Elective caesarian deliveries or inductions prior to 37.0 completed weeks will be considered separately.
- **Preeclampsia / eclampsia:** preeclampsia or eclampsia reported by maternal interview with confirmation in medical record or report by medical record only is captured.
- **Small for gestational age:** small for gestational age is defined as birth size (weight, length or head circumference) less than or equal to the 10th centile for sex and gestational age using standard pediatric CDC growth curves for full term or preterm infants (CDC, 2000; Olsen et al., 2010).
- **Minor structural defects:** a minor structural defect is defined as a defect which has neither cosmetic nor functional significance to the child (e.g., complete 2,3 syndactyly of the toes). Minor structural defects will be identified only through the study dysmorphology examination for live born infants using the study-specific checklist.

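### The Kaplan-Meier method for spontaneous abortion is carried over to stillbirth with no rule for live birth and no read-off time, so the reported rate need not be the prevalence the objective asks for

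*Protocol*

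**What the plan says.** Protocol section 7.7.3.1.2 describes the SAB analysis in full. For the rate: "Left-truncated Kaplan-Meier estimate at 20 weeks' gestation will be used to estimate the SAB rate in each of the cohorts". The only censoring it names is "right-censoring when a subject is lost-to-follow-up prior to 20 weeks". For the comparison: "The Cox proportional hazards regression models incorporating left truncation will be used to estimate the hazard ratio (HR) of different cohorts". The rule for stillbirth is then one sentence: "Stillbirth will be analyzed in a similar fashion".

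Section 7.7.2.4 sets the risk period: "stillbirth is defined as non-deliberate fetal death anytime in gestation at or after 20 weeks post-LMP". Section 6 sets the target: "Secondary objectives are to estimate and compare the prevalence of selected adverse pregnancy and infant outcomes".

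The protocol gives no stillbirth-only rate. Section 7.5.1 has only a combined figure ("the anticipated spontaneous abortion/stillbirth rate is 10" percent) and expects 231 pregnancies per cohort with a live birth. No competing-risk method appears anywhere in the document.

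**The concern.** The SAB method works because its window closes at 20 weeks, before live births matter. Stillbirth starts where that window ends, so neither the 20-week read-off nor the named censoring reason carries over. Follow-up has to run to delivery, and by then almost every woman has left the risk set through live birth.

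If those exits are coded as censoring, Kaplan-Meier treats the delivered women as still able to have a stillbirth later. Each late stillbirth is divided by the few women still pregnant. At any given week, 1 minus Kaplan-Meier cannot be below the cumulative incidence, and it exceeds it once a stillbirth follows a delivery.

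Two things are at stake. The per-cohort rate may not be the share of pregnancies ending in stillbirth. It may also hang on one late event, in cohorts where only a few stillbirths are expected.

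**Working it through.** **The plan's own figure.** The only number in the protocol that involves stillbirth is the combined SAB/stillbirth row of Table 7-4: 259 per group, 10% in the comparison group, relative risk 1.9 (10% v 19%), two-sided Fisher test at 0.05, 80% power. Exact calculation gives 80.2%, so it reproduces. It says nothing about stillbirth alone.

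**Inputs from the protocol.** 231 pregnancies with a live birth per cohort (section 7.5.1), a 10% preterm rate (Table 7-4), and entry early in pregnancy, since "it is estimated that subjects will be an average of 7-10 weeks post-LMP at the time of enrollment".

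**Assumed inputs, not in the protocol.** True stillbirth prevalence 0.5% to 2%, several patterns of stillbirth timing, a term delivery peak near 39 weeks, and in the simulations 245 pregnancies per cohort.

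**Step 1, two stillbirths by hand.** Take 231 live births plus one stillbirth at 24 weeks (233 at risk) and one late stillbirth when a share s of the 231 is still pregnant. The proportion is 2/233 = 0.86%. With live births censored,

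1 − KM = 1 − (1 − 1/233) × (1 − 1/(231s + 1)).

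| s still pregnant | at risk, 231s + 1 | 1 − KM | ratio to 0.86% |
|---|---|---|---|
| 50% | 116.5 | 1.28% | 1.5 |
| 35% | 81.85 | 1.65% | 1.9 |
| 25% | 58.75 | 2.12% | 2.5 |
| 10% | 24.1 | 4.56% | 5.3 |

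The two events are the same in every row. Only the number of other women who had already delivered changes.

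**Step 2, average size by timing and read-off week.** A weekly table over weeks 20 to 42 gives 1 − KM divided by true prevalence. The ratios barely move for a prevalence of 0.5% to 2%.

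| Assumed stillbirth timing | read at 39 wk | at 40 wk | at 42 wk |
|---|---|---|---|
| all before 37 weeks | 1.01 | 1.01 | 1.01 |
| constant weekly hazard | 1.03 | 1.08 | 1.18 |
| about 23% at 37 weeks or later | 1.01 | 1.14 | 1.42 |
| hazard rising linearly from 37 weeks | 1.02 | 1.16 | 1.49 |
| 45% at 37 weeks or later | 0.99 | 1.27 | 2.9 |
| hazard doubling weekly from 37 weeks | 0.94 | 1.25 | 3.1 |

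Ratios below 1 at 39 weeks arise because later stillbirths are not yet counted.

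**Step 3, simulation at cohort size.** With 245 pregnancies, left-truncated entry and 23% of stillbirths at term, mean 1 − KM at the end of follow-up is 0.65% for a true 0.5% and 1.32% for a true 1.0%, a ratio of about 1.3. At 40 weeks it is 0.54% and 1.06%, about 1.07.

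A harsher model spreads term stillbirths evenly over 37 to 41 weeks, with 20% to 50% of stillbirths at term and 1% risk. The mean ratio is then about 1.5 to 2.3 at the end of the curve and 1.07 to 1.18 at 40 weeks. A minority of cohorts drives the mean: among cohorts with any stillbirth the median ratio is 1.03 to 1.41.

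**Step 4, one late event.** In that harsher model about 14 of 245 women are still pregnant at 41 weeks. A stillbirth then adds about 1/14 = 7.1 points to 1 − KM, against 1/245 = 0.4 points as a proportion.

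**The case against.** The strongest reply is that the protocol never says live births are censored and leaves further detail to the SAP, where competing events and time horizons usually belong. The first part is true: censoring of live births is an inference from the copied method. But the protocol is not silent on the estimator. It names Kaplan-Meier and extends it to stillbirth, and an SAP that followed this in the ordinary way would report the wrong quantity.

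A reader might infer that the plan reads the stillbirth curve at 20 weeks, where it would be empty. It does not, because that read-off is tied to the SAB rate. The gap is that stillbirth has no read-off time at all.

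A reader might also infer that the stillbirth rate will be about doubled. The documents cannot support this, since they give neither rate nor timing. Doubling needs many late stillbirths and a curve read at about 41 to 42 weeks. Nor is the average bias large against the estimator's own noise: in the harsher model of step 3 it is under about 0.6 of the Kaplan-Meier estimate's standard deviation. Dividing by the smaller standard error of a simple proportion would make it look worse than it is.

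Two further points limit the concern. The Cox hazard ratio with live births censored is a valid cause-specific comparison, so the between-cohort analysis stands. The abstract's data analysis section also plans frequencies and percentages, and section 7.7.9 plans cumulative outcomes by cohort in interim reports, so raw stillbirth percentages should be visible. That softens the problem, but the named rate estimate in the final analysis would still not be prevalence and could disagree with those counts.

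**Conclusion.** The point holds for the absolute stillbirth rate in each cohort. Section 7.7.3.1.2 carries over an estimator that, on its natural reading, does not estimate the prevalence named in section 6, and it leaves open both the handling of live birth and the read-off time.

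Read at the end of follow-up, the overstatement is about 1.2 to 1.5 times under middle assumptions and 2 or more only if many stillbirths are late. At 40 weeks the ratio is 1.01 to 1.27 across the patterns tried, and there is almost no bias if nearly all stillbirths are preterm. All of these multiples rest on assumed timing. The sensitivity to a single late stillbirth does not need an average-bias argument and may matter more in cohorts this small.

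The hazard ratio is not affected. SAB is not materially affected either: live birth plays no part before 20 weeks, and a 5% elective termination rate moves that estimate only about 0.3 points (10.0% v 10.3%).

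**What to change.** In section 7.7.3.1.2, replace the one-sentence rule for stillbirth with an explicit one, and carry it into the SAP:

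- Report the stillbirth rate per cohort as cumulative incidence (Aalen-Johansen), with entry at the later of enrolment and 20 weeks, and live birth and elective termination as competing events. A simple proportion among pregnancies reaching 20 weeks would also serve.
- State that the 20-week read-off for SAB does not apply to stillbirth.
- Keep the left-truncated Cox model for the comparison and label its hazard ratio as cause-specific.
- Leave the SAB analysis as it is.

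The cost is wording in the protocol and SAP and a standard R function. No new data are needed, and the final report is not due until May 2033.
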